## 4.2 Exclusion Criteria

Patients meeting any of the following exclusion criteria are not to be enrolled in the study:

- Patients who are Ph+ ALL who are naive to therapy with an approved tyrosine kinase inhibitor.
- Prior exposure to  $\geq 350$  mg/m^2 of anthracycline (in doxorubicin equivalent dosing), or left ventricular fractional shortening less than 50%.
- Failure to have fully recovered (ie,  $\leq$  Grade 2 toxicity) from the effects of prior chemotherapy regardless of the interval since last treatment.
- Major surgery within 14 days before enrollment.
- Chemotherapy in the last 14 days. (Steroids or Intrathecal chemotherapy will be allowed).
- Systemic treatment, within 7 days before study enrollment, with strong inhibitors of CYP1A2 (fluvoxamine, enoxacin, ciprofloxacin), strong inhibitors of CYP3A (clarithromycin, telithromycin, itraconazole, voriconazole, ketoconazole, nefazodone, posaconazole) or strong CYP3A

inducers (rifampin, rifapentine, rifabutin, carbamazepine, phenytoin, phenobarbital), or use of Ginkgo biloba or St. John's wort.

- Uncontrolled intercurrent illness including, but not limited to ongoing or active infection, symptomatic congestive heart failure, or psychiatric illness/social situations that would limit compliance with study requirements. Patients receiving intravenous antibiotics for infections that are under control may be included in this study.
- Known allergy to any of the study medications, their analogues, or excipients in the various formulations of any agent.
- Inability to swallow oral medication, inability or unwillingness to comply with the drug administration requirements, or GI procedure that could interfere with the oral absorption or tolerance of treatment.
- Diagnosed or treated for another malignancy within 2 years before study enrollment or previously diagnosed with another malignancy and have any evidence of residual disease. Patients with nonmelanoma skin cancer or carcinoma in situ of any type are not excluded if they have undergone complete resection.
- Patient has  $\geq$  Grade 2 peripheral neuropathy.
- Participation in clinical trials with other investigational agents not included in this trial, within 14 days of the start of this trial and throughout the duration of this trial.
- Female patients who are breastfeeding or have a positive serum pregnancy test during the screening period or a positive urine pregnancy test on Day 1 before first dose of study drug.

## **5. TREATMENT PLAN**

All patients will start therapy within 4 weeks from the bone marrow biopsy.

Lumbar puncture with intrathecal chemotherapy will be performed on all patients on day 1 (+/-1 day) to evaluate for disease.

BM or peripheral blood blast will be collected for correlative studies (optional) prior to starting therapy. Details of therapy are as follows:

Vincristine 1.5 mg/m^2 to a maximum dose of 2 mg IV on days 1, 8, 15 and 22

Dexamethasone 10 mg/m^2 orally or intravenously on days 1-14

Doxorubicin 60 mg/m^2 on day 1 by IV bolus.

For patients without CNS involvement:

-Cytarabine 100 mg will be administered intrathecally on day 1 (+/-1 day)  
(cytarabine dose should be reduced to 50 mg if given through a central ommaya reservoir)

-Methotrexate 12 mg will be administered intrathecally on day 8 (+/-1 day)

For patients with CNS involvement:

-Cytarabine 100 mg will be administered intrathecally on day 1 (+/-1 day)  
(cytarabine dose should be reduced to 50 mg if given through a central ommaya reservoir)

-Triple intrathecal chemotherapy with cytarabine 30 mg, methotrexate 15 mg and hydrocortisone 15 mg on (Day 8, 15 and 22 (+/-1 day)).

A bone marrow biopsy/aspirate will be performed at D28 +/- 3 days. For patients in remission, and have an available donor for HCT should proceed to HCT and be removed from the protocol treatment. Patients will still be followed for survival and progression free survival. A second cycle of treatment may be administered at the investigators discretion.

Ixazomib will be administered orally once weekly on day 1, 8 and 15. The first 3 patients will receive 2.3 mg orally (dose level 1). Dose escalation or de-escalation

will then proceed as previously detailed. There will be no inpatient dose escalation.

Table (7) Ixazomib dosing

	Day	Oral Dosing (mg)
Dose level -1	1, 8, 15	1.5
Dose level 1	1, 8, 15	2.3
Dose level 2	1, 8, 15	3
Dose level 3	1, 8, 15	4

Supportive care:

All patients will receive antibacterial, antiviral, antifungal and pneumocystis carinii pneumonia (PCP) prophylaxis. Prophylaxis regimen may follow institutional guidelines. The following prophylaxis may be used as guidelines:

Quinolones for antibacterial prophylaxis e.g., levofloxacin 500 mg orally daily

Antiviral prophylaxis: acyclovir 800 mg orally twice daily

Antifungal prophylaxis: Fluconazole 400 mg orally daily, or Liposomal Amphotericin B 9 mg/kg IV once per week or Caspofungin 50 mg IV /daily

PCP prophylaxis with SS bactrim daily, pentamidine inhalation 300 mg monthly, dapsone 100 mg daily or mepron

## 6. DRUG INFORMATION

### 6.1 Description of Investigational Agents (ixazomib)

#### **Ixazomib Capsules**

The ixazomib drug product is provided in strengths of 4.0-, 3.0-, and 2.3-mg and 2.0-, 0.5-, and 0.2 mg capsules as the active boronic acid. The different dose

strengths are differentiated by both capsule size and color as described below:

Dose Strength	Capsule Size	Capsule Color
4.0 mg	Size 4	Ivory
3.0 mg	Size 3	Light gray
2.3 mg	Size 2	Light pink
2.0 mg	Size 2	Swedish orange
0.5 mg	Size 3	Dark green
0.2 mg	Size 4	White opaque

For additional details, please see the ixazomib IB.

All protocol-specific criteria for administration of study drug must be met and documented before drug administration. Study drug will be administered only to eligible patients under the supervision of the investigator or identified sub-investigator(s). Patients should be monitored for toxicity, as necessary, and doses of ixazomib should be modified as needed to accommodate patient tolerance to treatment; this may include symptomatic treatment, dose interruptions, and adjustments of ixazomib dose.

## **6.2 Study Drug Administration**

### Ixazomib Administration

All protocol-specific criteria for administration of study drug must be met and documented before drug administration. Study drug will be administered or dispensed only to eligible patients under the supervision of the investigator or identified subinvestigator(s). Patients should be monitored for toxicity, as necessary, and doses of ixazomib should be modified as needed to accommodate patient tolerance to treatment; this may include symptomatic treatment, dose interruptions, and adjustments of ixazomib dose (see Section 6.3).

Patients should be instructed to swallow ixazomib capsules whole, with water, and not to break, chew, or open the capsules. Study drug should be taken on an empty

stomach (no food or drink, except water) at least 1 hour before or 2 hours after a meal. Each capsule should be swallowed separately with a sip of water. Followed by 8 ounces (240 mL) of water.

Missed doses can be taken, as soon as the patient remembers, if the next scheduled dose is 72 hours or more away. A double dose should not be taken to make up for a missed dose. If the patient vomits after taking a dose, the patient should not repeat the dose but should resume dosing at the time of the next scheduled dose.

### Ixazomib Destruction

Investigational ixazomib (expired or end of study) should be destroyed according to the institution's standard operating procedure. Be sure to document removal and destruction on drug accountability logs.

Please refer to the Pharmacy Manual for additional instructions.

## **6.3 Doxorubicin**

**Source and Pharmacology:** An anthracycline antibiotic isolated from cultures of *Streptomyces peucetius*. The cytotoxic effect of doxorubicin on malignant cells and its toxic effects on various organs are thought to be related to nucleotide base intercalation and cell membrane lipid binding activities of doxorubicin. Intercalation inhibits nucleotide replication and action of DNA and RNA polymerases. The interaction of doxorubicin with topoisomerase II to form DNA-cleavable complexes appears to be an important mechanism of doxorubicin cytotoxic activity. Doxorubicin cellular membrane binding may affect a variety of cellular functions. Enzymatic electron reduction of doxorubicin by a variety of oxidases, reductases and dehydrogenases generate highly reactive species including the hydroxyl free radical (OH•). Free radical formation has been implicated in doxorubicin cardiotoxicity by means of Cu (II) and Fe (III) reduction at the cellular level. Cells treated with doxorubicin have been shown to manifest the characteristic morphologic changes associated with apoptosis or programmed cell death. Doxorubicin induced

apoptosis may be an integral component of the cellular mechanism of action relating to therapeutic effects, toxicities, or both. Doxorubicin serum decay pattern is multiphasic. The initial distributive  $t_{1/2}$  is approximately 5 minutes suggesting rapid tissue uptake of doxorubicin. The terminal  $t_{1/2}$  of 20 to 48 hours reflects a slow elimination from tissues. Steady-state distribution volumes exceed 20 to 30 L/kg and are indicative of extensive drug uptake into tissues. Plasma clearance is in the range of 8 to 20 mL/min/kg and is predominately by metabolism and biliary excretion. The P450 cytochromes which appear to be involved with doxorubicin metabolism are CYP2D6 and CYP3A4. Approximately 40% of the dose appears in the bile in 5 days, while only 5 to 12% of the drug and its metabolites appear in the urine during the same time period. Binding of doxorubicin and its major metabolite, doxorubicinol to plasma proteins is about 74 to 76% and is independent of plasma concentration of doxorubicin.

#### **Formulation and Stability:**

Doxorubicin is available as red-orange lyophilized powder for injection in 10 mg, 20 mg, 50 mg, 150 mg vials and a preservative-free 2 mg/mL solution in 10 mg, 20 mg, 50 mg, 75 mg, 200 mg vials.

 Contains lactose monohydrate, 0.9 NS, HCl to adjust pH to 3. The Adriamycin RDF® (rapid dissolution formula) also contains methylparaben 1 mg per each 10 mg of doxorubicin to enhance dissolution. Multiple dose vial contains lactose, 0.9% NS, HCl to adjust pH to 3.

#### **Aqueous Solution:**

Store refrigerated 2°-8°C (36°-46°F). Protect from light. Retain in carton until contents are used.

#### **Powder for Injection:**

Store unconstituted vial at room temperature 15°-30°C (59°-86°F). Retain in carton until contents are used. Reconstitute with preservative-free normal saline to

a final concentration of 2 mg/mL. After adding the diluent, the vial should be shaken and the contents allowed to dissolve. The reconstituted solution is stable for 7 days at room temperature under normal room light (100 footcandles) and 15 days under refrigeration 2°-8°C (36°-46°F). Protect from exposure to sunlight. Doxorubicin may be further diluted in 0.9%NaCl or dextrose containing solutions and administered by infusion.

**Guidelines for Administration:** See Treatment and Dose Modification sections of the protocol. Administer IV through the tubing of rapidly infusing solution of D5W or 0.9% NaCl preferably into a large vein. Protect the diluted solution from sunlight. To avoid extravasation, the use of a central line is suggested.

**Supplier:** Commercially available from various manufacturers. See package insert for further information.

### **Adverse effects**

Cardiovascular:

Acute cardiotoxicity: Atrioventricular block, bradycardia, bundle branch block, ECG abnormalities, extrasystoles (atrial or ventricular), sinus tachycardia, ST-T wave changes, supraventricular tachycardia, tachyarrhythmia, ventricular tachycardia

Delayed cardiotoxicity: LVEF decreased, CHF (manifestations include ascites, cardiomegaly, dyspnea, edema, gallop rhythm, hepatomegaly, oliguria, pleural effusion, pulmonary edema, tachycardia); myocarditis, pericarditis

Central nervous system: Malaise

Dermatologic: Alopecia, itching, photosensitivity, radiation recall, rash; discoloration of saliva, sweat, or tears

Endocrine & metabolic: Amenorrhea, dehydration, infertility (may be temporary), hyperuricemia

Gastrointestinal: Abdominal pain, anorexia, colon necrosis, diarrhea, GI ulceration, mucositis, nausea, vomiting

Genitourinary: Discoloration of urine

Hematologic: Leukopenia/neutropenia (75%; nadir: 10-14 days; recovery: by day 21); thrombocytopenia and anemia

Local: Skin “flare” at injection site, urticaria

Neuromuscular & skeletal: Weakness

Postmarketing and/or case reports: Anaphylaxis, azoospermia, bilirubin increased, coma (when in combination with cisplatin or vincristine), conjunctivitis, fever, gonadal impairment (children), growth failure (prepubertal), hepatitis, hyperpigmentation (nail, skin & oral mucosa), infection, keratitis, lacrimation, myelodysplastic syndrome, neutropenic fever, neutropenic typhlitis, oligospermia, peripheral neurotoxicity (with intra-arterial doxorubicin), phlebosclerosis, radiation recall pneumonitis (children), secondary acute myelogenous leukemia, seizure (when in combination with cisplatin or vincristine), sepsis, shock, Stevens-Johnson syndrome, systemic hypersensitivity (including urticaria, pruritus, angioedema, dysphagia, and dyspnea), toxic epidermal necrolysis, transaminases increased, urticarial

Supportive Care:

Cardio Protective: Dexaroxane may be used and dosed per institutional standards

## 6.4 Vincristine

**Source and Pharmacology:** Vincristine is an alkaloid isolated from *Vinca rosea* Linn (periwinkle). It binds to tubulin, disrupting microtubules and inducing metaphase arrest. Its serum decay pattern is triphasic. The initial, middle, and terminal half-lives are 5 minutes, 2.3 hours, and 85 hours respectively; however, the range of the terminal half-life in humans is from 19 to 155 hours. The liver is the

major excretory organ in humans and animals; about 80% of an injected dose of vincristine sulfate appears in the feces and 10% to 20% can be found in the urine. The P450 cytochrome involved with vincristine metabolism is CYP3A4. Within 15 to 30 minutes after injection, over 90% of the drug is distributed from the blood into tissue, where it remains tightly, but not irreversibly bound. It is excreted in the bile and feces. There is poor CSF penetration.

**Formulation and Stability:**

Vincristine is supplied in a vial each mL of which contains vincristine sulfate, 1 mg (1.08  $\mu$ mol); mannitol, 100 mg; Sterile Water for Injection; acetic acid and sodium acetate are added for pH control. The pH of Vincristine Sulfate Injection, *USP* ranges from 3.5 to 5.5. This product is a sterile solution. Store refrigerated at 2°-8°C or 36°-46°F. Protect from light and retain in carton until time of use. Do not mix with any IV solutions other than those containing dextrose or saline.

**Guidelines for Administration:**

See Treatment and Dose Modifications sections of protocol.

The World Health Organization, the Institute of Safe Medicine Practices (United States) and the Safety and Quality Council (Australia) all support the use of minibag rather than syringe for the infusion of vincristine. The delivery of vincristine via either IV slow push or minibag is acceptable. Injection of vincristine sulfate should be accomplished as per institutional policy. Vincristine sulfate must be administered via an intact, free-flowing intravenous needle or catheter. Care should be taken to ensure that the needle or catheter is securely within the vein to avoid extravasation during administration. The solution may be injected either directly into a vein or into the tubing of a running intravenous infusion.

***When dispensed the container or syringe containing vincristine must be enclosed in an overwrap bearing the statement “DO NOT REMOVE COVERING UNTIL MOMENT OF INJECTION. FATAL IF GIVEN INTRATHECALLY. FOR INTRAVENOUS USE ONLY.”***

**Supplier:**

Commercially available from various manufacturers. See package insert for more detailed information.

**Adverse Effects:**

Cardiovascular: Edema, hyper-/hypotension, MI, myocardial ischemia

Central nervous system: Ataxia, coma, cranial nerve dysfunction (auditory damage, extraocular muscle impairment, laryngeal muscle impairment, paralysis, paresis, vestibular damage, vocal cord paralysis), dizziness, fever, headache, neurotoxicity (dose-related), neuropathic pain (common), seizure, vertigo

Dermatologic toxicity: Alopecia (common), rash

Endocrine & metabolic: Hyperuricemia, parotid pain, SIADH (rare)

Gastrointestinal: Abdominal cramps, abdominal pain, anorexia, constipation (common), diarrhea, intestinal necrosis, intestinal perforation, nausea, oral ulcers, paralytic ileus, vomiting, weight loss

Genitourinary: Bladder atony, dysuria, polyuria, urinary retention

Hematologic: Anemia (mild), leukopenia (mild), thrombocytopenia (mild), thrombotic thrombocytopenic purpura

Hepatic: Hepatic sinusoidal obstruction syndrome (SOS; veno-occlusive liver disease)

Local: Phlebitis, tissue irritation/necrosis (if infiltrated)

Neuromuscular & skeletal: Back pain, bone pain, deep tendon reflex loss, difficulty walking, foot drop, gait changes, jaw pain, limb pain, motor difficulties, muscle wasting, myalgia, paralysis, paresthesia, peripheral neuropathy (common), sensorimotor dysfunction, sensory loss

Ocular: Cortical blindness (transient), nystagmus, optic atrophy with blindness

Otic: Deafness

Renal: Acute uric acid nephropathy, hemolytic uremic syndrome

Respiratory: Bronchospasm, dyspnea, pharyngeal pain

Miscellaneous: Allergic reactions (rare), anaphylaxis (rare), hypersensitivity (rare)

## **6.5 Dexamethasone**

**Source and Pharmacology:** Dexamethasone is a synthetic fluorinated glucocorticoid devoid of mineralocorticoid effects. Dexamethasone, 0.75 mg, has potent anti-inflammatory activity equivalent to approximately 5 mg of prednisone. Glucocorticoids produce widespread and diverse physiologic effects on carbohydrate, protein, and lipid metabolism, electrolyte and water balance, functions of the cardiovascular system, kidney, skeletal muscle, and the nervous systems. Glucocorticoids reduce the concentration of thymus-dependent lymphocytes (T-lymphocytes), monocytes, and eosinophils. Glucocorticoids selectively bind to the cortisol receptors on human lymphoid cells which are found in larger numbers on leukemic lymphoblasts. They also decrease binding of immunoglobulin to cell surface receptors and inhibit the synthesis and/or release of interleukins, thereby decreasing T-lymphocyte blastogenesis and reducing expansion of the primary immune response. The specific cellular mechanisms that act to halt DNA synthesis are thought to be related to inhibition of glucose transport or phosphorylation, retardation of mitosis, and inhibition of protein synthesis. Elimination half-lives for the following age groups have been reported to be: infants and children under 2 years of age: 2.3 to 9.5 hours, 8 to 16 years: 2.82 to 7.5 hours, and adults (age not specified): 3 to 6 hours. The biologic half-life is 36- 72 hours. It is primarily metabolized in the liver and excreted by the kidneys.

### **Formulation and Stability:**

Available in 0.25 mg, 0.5 mg, 0.75 mg, 1 mg, 1.5 mg, 2 mg, 4 mg, and 6 mg tablets; liquid formulations are available in 0.5 mg/5 mL and 0.5 mg/0.5 mL concentration. Inactive ingredients vary depending on manufacturer but tablet formulations may include: calcium or magnesium stearate, corn starch, lactose, and various dyes. Liquid formulations may include: 5%-30% alcohol, benzoic acid, sorbitol, sodium saccharin, glycerin, purified water, and various dyes. Dexamethasone Sodium Phosphate Solution for Injection is available as 4 mg/mL, 10 mg/mL, 20 mg/mL and 24 mg/mL. Four milligrams of dexamethasone sodium phosphate is equivalent to 3.33 mg of dexamethasone. Vial sizes include 1 mL, 5 mL, 10 mL, 25 mL, and 30 mL and are available in multi-dose vials as well as unit of use vials and syringes. Inactive ingredients vary depending on manufacturer but include creatinine, sodium and propyl paraben, benzyl alcohol, and EDTA.

**Guidelines for Administration:**

See Treatment and Dose Modifications section of the protocol.

Dexamethasone Sodium Phosphate for Injection may be given IV, or IM undiluted. For IV use, it may be further diluted in dextrose or saline containing solutions. Avoid benzyl alcohol containing dexamethasone solutions for use in neonates. Diluted solutions that contain no preservatives should be used within 24 hours, but maintain stability for at least 14 days in PVC bags at room temperature protected from light.

**Supplier:**

Commercially available from various manufacturers. See package insert for further information

**Adverse effects:**

Cardiovascular: Arrhythmia, bradycardia, cardiac arrest, cardiomyopathy, CHF, circulatory collapse, edema, hypertension, myocardial rupture (post-MI), syncope, thromboembolism, vasculitis

Central nervous system: Depression, emotional instability, euphoria, headache, intracranial pressure increased, insomnia, malaise, mood swings, neuritis, personality changes, pseudotumor cerebri (usually following discontinuation), psychic disorders, seizure, vertigo

Dermatologic: Acne, allergic dermatitis, alopecia, angioedema, bruising, dry skin, erythema, fragile skin, hirsutism, hyper-/hypopigmentation, hypertrichosis, perianal pruritus (following I.V. injection), petechiae, rash, skin atrophy, skin test reaction impaired, striae, urticaria, wound healing impaired

Endocrine & metabolic: Adrenal suppression, carbohydrate tolerance decreased, Cushing's syndrome, diabetes mellitus, glucose intolerance decreased, growth suppression (children), hyperglycemia, hypokalemic alkalosis, menstrual irregularities, negative nitrogen balance, pituitary-adrenal axis suppression, protein catabolism, sodium retention

Gastrointestinal: Abdominal distention, appetite increased, gastrointestinal hemorrhage, gastrointestinal perforation, nausea, pancreatitis, peptic ulcer, ulcerative esophagitis, weight gain

Genitourinary: Altered (increased or decreased) spermatogenesis

Hepatic: Hepatomegaly, transaminases increased

Local: Postinjection flare (intra-articular use), thrombophlebitis

Neuromuscular & skeletal: Arthropathy, aseptic necrosis (femoral and humeral heads), fractures, muscle mass loss, myopathy (particularly in conjunction with neuromuscular disease or neuromuscular-blocking agents), neuropathy, osteoporosis, paresthesia, tendon rupture, vertebral compression fractures, weakness

Ocular: Cataracts, exophthalmos, glaucoma, intraocular pressure increased

Renal: Glucosuria

Respiratory: Pulmonary edema

Miscellaneous: Abnormal fat deposition, anaphylactoid reaction, anaphylaxis, avascular necrosis, diaphoresis, hiccups, hypersensitivity, impaired wound healing, infections, Kaposi's sarcoma, moon face, secondary malignancy

## **7. DOSE-MODIFICATION GUIDELINES**

### **7.1 Recommended ixazomib Criteria for Beginning or Delaying a Subsequent Treatment Cycle & Dose Modifications for Treatment Associated Toxicity**

- Treatment with ixazomib will use a cycle length of 28 days.

All non-hematological toxicity considered to be related to treatment with ixazomib must have resolved to  $\leq$  Grade 1, to the patient's baseline values, or to a level considered acceptable by the physician (eg, hypokalemia that can be managed by replacements) before the next dose of ixazomib could be given. There will be no dose modifications or delays for hematological toxicity as all patients will experience neutropenia and/or thrombocytopenia with the VXD regimen. In the pediatric study, Grade 3 or 4 neutropenia and thrombocytopenia occurred in 97.6 and 79.8% of patients treated with VXLD respectively.

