### **7.5 Criteria for Toxicity Recovery for a New Cycle of Therapy to Begin:**

- Absolute neutrophil count (ANC) > 1,000/cmm and platelets > 75,000/cmm unless the cytopenias are secondary to disease
- All other nonhematologic toxicity (except for alopecia) must have resolved to ≤Grade 1 or to the patient's baseline condition.

If the patient fails to meet the above criteria for retreatment, hold treatment. The patient should be re-evaluated weekly or more frequently to determine whether the criteria for retreatment have been met and a new cycle can begin. If the criteria for retreatment have been met refer to the appropriate drug modification guidelines to resume therapy.

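### Read literally, Sections 7.1 and 7.5 give opposite instructions for starting cycle 2 in a patient with treatment-related cytopenia

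*Combined protocol and SAP*

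**What the plan says.** Section 7.1 is headed "Recommended ixazomib Criteria for Beginning or Delaying a Subsequent Treatment Cycle & Dose Modifications for Treatment Associated Toxicity". It sets a 28-day cycle and gives a recovery rule for ixazomib-related non-hematologic toxicity that must be met "before the next dose of ixazomib could be given". On blood counts it then says: "There will be no dose modifications or delays for hematological toxicity as all patients will experience neutropenia and/or thrombocytopenia with the VXD regimen". That sentence carries no limit to particular days or cycles.

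Section 7.5 is headed "Criteria for Toxicity Recovery for a New Cycle of Therapy to Begin". It requires an ANC above 1,000/cmm and "platelets > 75,000/cmm unless the cytopenias are secondary to disease". The consequence is explicit: "If the patient fails to meet the above criteria for retreatment, hold treatment". The patient is then reassessed at least weekly. Once the criteria are met, the reader is sent to the relevant drug modification guidelines.

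A second cycle is provided for. The Protocol Summary, Section 3 and Section 5 allow repeat treatment, and the Schedule of Events has a column for week 1 of cycles 1 and 2.

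**The concern.** Both sections, by their headings, speak to the start of a further cycle. One rules out a delay for low counts; the other requires it. An investigator with a patient due for cycle 2 and still cytopenic from treatment can cite the protocol for either course.

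Two things are at stake. The first is safety at retreatment, because the protocol does not settle whether treatment-related cytopenia stops a new cycle. The second is the cycle 2 data. Tolerability is part of the primary objective (Section 2.1), and Section 14.1 summarizes adverse events by dose level. Under the 3+3 scheme a dose level normally holds three to six patients, so one patient is 1/6 (17%) to 1/3 (33%) of a cohort. If patients are retreated under different readings, differences in cycle 2 toxicity or delivered dose between levels could partly reflect the reading used.

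**Working it through.** The point rests on comparing two rules; no power or sample-size calculation applies.

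**Step 1. The two rules side by side**

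| | Section 7.1 | Section 7.5 |
|---|---|---|
| Scope in heading | Ixazomib: start or delay of a subsequent cycle, and dose modification | Start of a new cycle of therapy |
| Low counts due to treatment | No delay, no dose change | Hold until ANC > 1,000/cmm and platelets > 75,000/cmm |
| Low counts due to disease | No separate rule | Exempt from the hold |
| Limited to doses within a cycle? | Not stated | No, addresses new cycles only |

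**Step 2. Apply both at day 1 of cycle 2**

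- Counts above both thresholds: neither section delays treatment. No conflict.
- Counts at or below a threshold, attributed to disease: 7.5 exempts the patient. No conflict.
- Counts at or below a threshold, attributed to treatment: 7.5 holds the cycle, while 7.1 read literally does not allow ixazomib to be delayed. Ixazomib is part of the cycle being held, so both cannot be followed.

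Only the third group is in conflict. The protocol's own definitions show that such patients can exist. Appendix 18.2 defines CR without platelet recovery as fewer than 5% marrow blasts with platelets below 75,000/µl. If such a patient has no donor, is offered a second cycle, and the low platelets are put down to treatment, the two sections disagree.

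**Step 3. Check the figures that 7.1 cites**

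From Table (1) in Section 1.1 (VXLD, n = 124):

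- Grade 3 or 4 neutropenia: 121/124 = 97.6%, as stated.
- Grade 3 or 4 thrombocytopenia: 99/124 = 79.8%, as stated.
- At least one of the two: from max(121, 99)/124 = 97.6% to min(124, 121 + 99)/124 = 124/124 = 100%.

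These are the proportions of children who had the toxicity at some time on a regimen that included pegaspargase. They are not counts in adults on VXD when cycle 2 is due. Section 6.3 gives the neutrophil nadir after doxorubicin as 10-14 days, with recovery by day 21. The size of the third group in Step 2 therefore cannot be calculated.

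**Step 4. Which part of the trial is touched**

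Section 7.5 says nothing about doses on days 8 and 15, so cycle 1 has only one rule on counts. Section 3 closes the DLT window 28 days after the first ixazomib dose, which is the length of one cycle. The conflict therefore starts at cycle 2.

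**The case against.** The best defence is that the two sections divide the work: 7.1 covers ixazomib doses within a cycle, and 7.5 decides whether a new cycle of the whole regimen starts. Several features support this. Section 7.1 frames its recovery rule around the next ixazomib dose. Its reason for not delaying, expected cytopenia on VXD, fits days 8 and 15. Section 7.5 is the specific section on new cycles, and its count thresholds would do little if 7.1 barred every hematologic hold. Its closing sentence also implies an order: first meet the 7.5 criteria, then turn to the drug guidelines.

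Much of this stands, and it may well be what the authors meant. It does not remove the conflict. The first dose of cycle 2 is also a next dose of ixazomib. The 7.1 heading expressly names a subsequent cycle, and its no-delay sentence has no limit. The closing sentence of 7.5 applies once its criteria are met and does not narrow 7.1. The reader has to supply the division.

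A reader might also see a second contradiction in non-hematologic recovery, because 7.1 accepts Grade 1, baseline, "or to a level considered acceptable by the physician", while 7.5 requires Grade 1 or baseline. That does not hold. Section 7.5 is the stricter rule, and a patient who meets it also meets 7.1, so both can be followed.

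**Conclusion.** The point holds in a limited form. On their face, 7.1 and 7.5 conflict for the first ixazomib dose of cycle 2 in a patient whose low counts are due to treatment. This assumes that the 7.1 heading means what it says and that its sentence is read as written. Under the within-cycle reading the conflict disappears, but the documents do not state that reading.

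The effect is on safety at retreatment and on tolerability data from cycle 2 onward, in an unknown number of patients. A second cycle is discretionary, and patients in CR who are eligible for transplant leave for HSCT.

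Three stronger inferences are not supported:

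- **That nearly every patient is affected.** The 97.6% and 79.8% are pediatric VXLD incidences, not counts when cycle 2 is due.
- **That sites would diverge.** Section 15.2 treats multisite conduct only as a possibility.
- **That the MTD is compromised.** Under Section 3 the DLT window closes before cycle 2 toxicity can count. Section 16.1 instead ends the window 28 days after the last dose. Counted from a day 15 dose, that is day 15 + 28 = day 43, which could overlap cycle 2. That disagreement between Sections 3 and 16.1 is a separate matter, and this point does not depend on it.

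**What to change.** Reconcile Sections 7.1 and 7.5. State the scope of the no-delay sentence in 7.1, that is, whether it applies to doses within a cycle, to the start of a new cycle, or to both. State which section governs the start of a new cycle, and add a cross-reference in each. If the scope of 7.1 is narrowed, bring its heading into line. The clinical team must choose the rule; no threshold or rule is proposed here.

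The cost is protocol wording only. Sample size, dose levels and the planned analysis do not change. No new data are needed, because the Schedule of Events already includes a CBC in week 1 of cycles 1 and 2.
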